Our single arm SCOUTS2 pilot study showed some success of a combination of 1) early CPAP technical support, 2) motivational enhancement therapy (MET) directed toward the patient, and 3) follow-up phone interviews to provide adherence feedback and enhance self-management skills, on CPAP use in post-stroke patients.²⁶ To maximize adherence and develop a more generalizable protocol, additional work is needed to adapt and supplement these interventions for stroke patients, who often have cognitive, language, and physical dysfunction. The goal of this application is to adapt the three promising and scalable interventions of the SCOUTS2 pilot study²⁶ for stroke patients with OSA identified in an IPR setting, and to supplement this with MET directed toward a CPAP partner and mobile health (mHealth). Using self-determination theory (SDT), we will adapt these intervention components using a human-centered design approach to create a package of interventions to improve CPAP use. Following adaptation, we will (in a separate, future, IRB application) rigorously test the effectiveness of this multicomponent intervention on CPAP adherence among stroke patients within a randomized controlled trial (RCT).

Goals and objectives

Aim 1a: To adapt and refine the existing SCOUTS2 adherence interventions (CPAP technical support, MET, and phone follow-up) for stroke patients with OSA. Disability related to stroke, including arm/hand, language, and cognitive dysfunction, affects stroke patients' ability to engage in interventions used in the general population to increase CPAP use. We will adapt CPAP adherence interventions iteratively, with input from stroke patients treated with CPAP on IPR, to increase CPAP use.

Aim 1b: To develop theory-driven, tailored mHealth messages to motivate stroke patients to use CPAP. Using SDT, we will develop and adapt a library of tailored messages designed to improve perceived autonomy, relatedness, and competence regarding CPAP use after stroke. Tailored text, e-mail or phone messages, delivered via a web-based application, will be refined after initial pretesting among stroke patients.

Aim 1c: To implement MET to partners of stroke participants treated with CPAP. Using MET counseling sessions during IPR, we will train CPAP partners to deliver autonomy-based support to patients with stroke.

Significance

Aim 1a. Adaptation of existing intervention components

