Stroke patients on Neurology and PM&R will be screened for eligibility and interested eligible patients will be consented. While on either of two IPR units at the University of Washington (UW) or Harborview Medical Center (HMC), consented participants will be tested for OSA, and then, within a single-arm study, exposed to a multicomponent CPAP adherence intervention, beginning during IPR and extending for 3 months. Throughout the intervention exposure, participants' CPAP use will be monitored, and input regarding the intervention will be sought from the participants, CPAP partners (ideally bedpartners, but if not available, then those who can provide support to the patient), and the research team implementing the intervention (sleep technologist, research coordinator, sleep coach, nurses). Semi-structured interviews will take place to obtain formal feedback from participants at three time points during their 3-month intervention. Data will be reviewed in meetings with the study team and a patient advisory board, and adaptations will be devised and then implemented within the next batch of Aim 1 participants. Through this iterative process that includes input from important stakeholders, the behavioral intervention will be adapted for use among stroke patients.

Participants and eligibility criteria

60 adult patients recovering from acute stroke within the past 30 days will be recruited during inpatient acute or IPR (2 IPR units) stroke stays.

Inclusion criteria include:

1. Age 18 years or older
2. Head CT or brain MRI demonstrating an acute ischemic infarction or intraparenchymal hemorrhage within past 30 days
3. Person providing consent (patient or legally authorized representative) able to be consented in English or Spanish.

Exclusion criteria include:

1. Unable to obtain informed consent from participant or surrogate in English or Spanish
2. Incarcerated
3. Known pregnancy
4. Current mechanical ventilation, tracheostomy or supplemental oxygen use > 4L/min
5. Current use of positive airway pressure or use within 14 days prior to stroke
6. History of pneumothorax, bullous emphysema or other serious co-morbid conditions which limit CPAP use
7. Stroke related to tumors, vascular malformations or subarachnoid hemorrhage

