Nox T3s data will be uploaded for review by a scoring team at Elite Sleep Professionals, or similar organization of registered polysomnographic technologists. The sleep apnea tests will not be reviewed by a physician. Study participants who are eligible for the CPAP adherence intervention will not be told of the severity of OSA until completion of study participation so that any decision to adhere to CPAP is not influenced by OSA severity from a single-night HSAT, which typically underestimates the disease severity.³⁸⁻⁴⁰ Nox T3s reports will be provided to the participant and the clinical team at the time the participant exits participation in this study. Based upon prior studies in this population^{4-6 17} we anticipate that about 20% of the 60 participants with completed OSA tests may be excluded based on these criteria, yielding approximately 48 participants for the Aim 1 adherence program adaptation.

Existing SCOUTS2 adherence intervention, implemented for participants

Participants who meet criteria for a diagnosis of OSA will be set up with CPAP on the next available night after the HSAT by study staff led by the study's sleep technologist, who will provide mask fitting and CPAP exposure during the daytime prior to the 1st night of CPAP use. The CPAP device (AirSense™ 11 AutoSet, ResMed) includes an auto-titrator that can adjust the delivered pressure between 4 to 20 cm of water to eliminate obstructive events. Pressure settings may be narrowed. All Aim 1 participants may receive 3 basic supportive treatments to approximate the care provided after a sleep clinic or in-hospital diagnosis of OSA: 1) education on OSA and the importance of CPAP treatment for improved sleep and vascular health; 2) standard inpatient CPAP support from respiratory therapy and IPR nurses for mask placement and adjustments; and 3) outpatient access to a national durable medical equipment (DME) company, for issues that may arise with CPAP at home. Participants may also receive 3 behavioral adherence interventions:

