For aphasic participants, the sleep coach will use published recommendations to adapt MET sessions for people with stroke-related aphasia, including strategies to enhance language comprehension and facilitate

expression⁴⁷⁻⁴⁹ and patient-specific strategies recommended by the study participant's speech-language pathologists on the IPR unit. Patients with more severe aphasia with complete incomprehension are not typically admitted to IPR. The MET for aphasic participants will include two face-to-face sessions during IPR, each lasting about 30 to 60 minutes, and one ~20-minute phone session with inclusion of the CPAP partner, when possible. Face-to-face sessions will incorporate MET components used in non-aphasic participants but will focus on information exchange through visual aids, exploring potential barriers to CPAP use through enhanced communication and goal setting.⁵⁰ MET sessions may be bolstered by individualized written and visual feedback regarding the OSA testing, potential vascular consequences, and CPAP download data illustrating the effectiveness of treatment in reducing respiratory events.

Fidelity for the MET sessions will be evaluated in multiple ways. Some MET sessions will be recorded, uploaded for processing, and reviewed via the cloud-based and HIPAA-compliant Lyssn platform, which supports training and quality assurance by providing automated transcription and fidelity feedback from a session recording. The recordings are processed through the system's artificial intelligence analytics tool and automatically transcribed via speech-to-text transcription. The platform will produce reports of each session, including general and specific metrics for MET. The sessions will be evaluated through the Lyssn platform and feedback reports will be provided to the sleep coach. Consultants, [name] and [name], may also review ~20% of the counseling sessions for non-aphasic participants utilizing a MET checklist to provide feedback to the sleep coach via quarterly virtual meetings.²⁰ Co-I [name], who has adapted motivational counseling to improve adherence to therapy in other populations,⁵¹ may review ~20% of the recordings of aphasic participants utilizing a modified MET checklist.

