Our adaptation approach will be guided by the simple and iterative Discover, Design and Build, and Test (DDBT) framework for psychosocial and health behavior change intervention development and adaptation stemming from a human-centered design perspective.⁵² The DDBT approach aims to maintain the core components of interventions while improving usability for specific populations (here, stroke patients with OSA) and implementation outcomes in specific settings (here, acute IPR and in the home).⁵³⁻⁵⁹ (i) The **Discovery** phase seeks to identify facilitators and barriers of contextual usability among stakeholders. This phase will initially involve interviews of participants, their CPAP partners, when available, and intervention staff (sleep technologist, sleep coach, and research coordinator) to explore CPAP barriers and facilitators through structured and open-ended feedback opportunities. Interviews with participants and CPAP partners lasting approximately 30 minutes will occur typically after the first 3 days of CPAP technical support, at the end of IPR to evaluate the MET and mHealth interventions and at the end of the 3-month treatment period to assess outpatient and prior IPR treatments. Interviews with the intervention staff, occurring quarterly from the beginning to the end of aim 1 and lasting approximately 20 minutes, will focus on feedback about the content, process and feasibility of each intervention.⁶⁰ The study team will analyze after about 6 months of recruitment the participant interviews and adherence patterns after completion of an estimated 15 of the 3-day interviews, 13 of the end-of-IPR interviews and 8 of the 3-month interviews. Analysis of participant, CPAP partner and staff interviews along with adherence and engagement data will feed Discovery. (ii) The **Design and Build** phase uses the Discovery information to iteratively refine the intervention and implement strategies to address the unique barriers faced by stroke IPR patients as they work to engage with the intervention components to successfully and consistently use CPAP. Refinements in Aim 1 will involve iterative and collaborative content and delivery adaptation by the study team based on the Discovery data above. The study team will present adaptation proposals to a stroke patient advisory board. This may be repeated as needed. After approximately 6 months of recruitment, researchers will review interview feedback with the patient advisory board and present proposed adaptations to the interventions. The patient advisory board will review these proposals and make recommendations for adapting the behavioral interventions. (iii) The **Test** phase evaluates the intervention's user experience, satisfaction, and implementation outcomes. The adapted intervention will be tested on the next 12 participants over an estimated 4 months. The iterative DDBT cycle will be repeated, with results being presented again to the patient advisory board with additional adaptation feedback, as needed. We will conduct 'think-aloud' cognitive interviews with the next approximately 5 participants while they interact with the intervention components to elicit organic reactions to the intervention and reveal any final needed adaptations.^{61,62}

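### The final think-aloud step takes about five participants in order of arrival, so the last usability check may include nobody with aphasia

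*Combined protocol and SAP*

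**What the plan says.** Aim 1a (Goals and objectives) bases the adaptation on stroke deficits: "Disability related to stroke, including arm/hand, language, and cognitive dysfunction, affects stroke patients' ability to engage in interventions used in the general population". The MET component, item (ii) of the adherence intervention, then sets out a separate format for one of these groups: "the sleep coach will use published recommendations to adapt MET sessions for people with stroke-related aphasia". That format has its own session plan and relies on visual aids, and Visit 9 of the visit schedule repeats it. Visit 11 and the mHealth section add app coaching for participants with aphasia, cognitive deficits or dexterity problems.

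In Adaptation and refinement, the Test phase fills both of its steps by sequence. For the batch: "The adapted intervention will be tested on the next 12 participants over an estimated 4 months". For the final step: "We will conduct 'think-aloud' cognitive interviews with the next approximately 5 participants while they interact with the intervention components". The stated purpose of the final step is to find whatever adaptations are still needed. Neither this section nor any other sets a quota, a purposive rule or a minimum number by type of deficit. Statistical analysis names no analysis of interview themes by deficit.

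Aphasia is not an exclusion criterion and a representative may consent, so people with aphasia can enter the study.

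**The concern.** A participant without aphasia does not receive the aphasia format of MET and so cannot reveal what is wrong with it. If the last five participants all lack aphasia, that format goes forward to the planned randomised trial without having been seen in the step meant to catch remaining problems.

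There is also a practical difficulty. A think-aloud interview depends on speech, and the section describing it mentions no communication support. A participant with aphasia who does arrive among the five may therefore contribute less than the step needs.

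**Working it through.** **Inputs from the documents**
- Enrolment (Participants and eligibility criteria): "60 adult patients recovering from acute stroke within the past 30 days will be recruited".
- Expected loss after sleep testing (Screening for OSA): "we anticipate that about 20% of the 60 participants with completed OSA tests may be excluded based on these criteria". The same section puts the number left for adaptation at about 48.
- Test batch 12 and think-aloud about 5, both consecutive (Adaptation and refinement).
- Pace: an estimated 15 three-day interviews after about 6 months of recruitment (same section).

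**The plan's own figure.** 60 × (1 − 0.20) = 48, which agrees with the protocol. The documents give no justification for the 12 or the 5, so there is no further calculation to reproduce.

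**Assumption.** The documents state no aphasia share, p, so it is varied from 10% to 40%. The MET section says that the most severe aphasia is not typically admitted to inpatient rehabilitation, which argues against relying on a high share.

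**Chance of no participant with aphasia among n consecutive entrants:** (1 − p)^n. For example, at p = 0.20 and n = 5, 0.80^5 = 0.328. The chance of at most one of five adds 5p(1 − p)^4.

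| Assumed share p | None of 5 | At most 1 of 5 | None of 12 | None of 12 + 5 = 17 |
|---|---|---|---|---|
| 10% | 59.0% | 91.9% | 28.2% | 16.7% |
| 20% | 32.8% | 73.7% | 6.9% | 2.3% |
| 30% | 16.8% | 52.8% | 1.4% | 0.2% |
| 40% | 7.8% | 33.7% | 0.2% | 0.02% |

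**Sensitivity to the finite pool.** Drawing 5 without replacement from 48, the chance of none is C(48 − k, 5)/C(48, 5), where k is the number with aphasia. This gives 56.2%, 29.3%, 16.3% and 6.9% for k = 5, 10, 14 and 19, close to the binomial figures.

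**Share needed for order of arrival to be adequate.** Solving (1 − p)^5 ≤ 0.10 gives p ≥ 1 − 0.10^(1/5) = 36.9%. For a 5% risk, p ≥ 1 − 0.05^(1/5) = 45.1%.

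**Time cost of reserving places.** The pace is 15/6 = 2.5 participants per month, so any five take 5/2.5 = 2.0 months. The mean wait for two participants with aphasia is 2/(2.5p): 8.0 months at 10%, 4.0 at 20% and 2.7 at 30%. For one it is 1/(2.5p): 4.0, 2.0 and 1.3 months. The test batch implies a slightly faster pace (12/4 = 3 per month), at which two take 3.3 months at 20% and 2.2 at 30%.

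**The case against.** The strongest reply is that people with aphasia are well represented elsewhere. The primary endpoint is the set of themes from the semi-structured interviews, not the think-aloud step. Those interviews take place at three time points and include CPAP partners where available. Staff are interviewed quarterly to the end of Aim 1, and about 20% of the MET recordings of participants with aphasia may be reviewed with a modified checklist. This stands, and it limits the point to one step. It does not close the gap. The initial interviews show what should change, and recording review checks the coach's delivery. Neither replaces watching a participant with aphasia use the adapted materials at the end.

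A second reply is that taking consecutive participants is a legitimate choice in a small formative study. It is. But no inferential estimate rests on consecutive entry here, so purposive choice loses nothing of that kind and suits a step designed to find problems.

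A reader might also infer that aphasia supports are planned for MET alone. They are not: Visit 11 and the mHealth section extend speech-language strategies and caregiver help to app coaching, and a proxy may help with the baseline and discharge assessments. What is missing is any mention of supports for the think-aloud interview.

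**Conclusion.** The concern holds for the final think-aloud step. With about five consecutive participants, the chance that none has aphasia is between 8% and 59% for assumed shares of 40% down to 10%. Only a share near 37% or more would bring it to 10% or below. The figures rest on that assumed share and on treating arrivals as independent. A change of wording is worthwhile before this step starts.

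Three stronger readings are tempting, and the documents do not support them:
- *The study could not meet Aim 1a for people with aphasia.* Aim 1a promises iterative adaptation with patient input, not a usability result specific to aphasia, and that input also comes through the three interviews.
- *The batch of 12 is equally exposed.* At shares of 20% or more it has none with probability 6.9% or less. Only at about 10% does the chance become material (28%).
- *Five participants without aphasia would be those who needed least adaptation.* They may have the arm/hand or cognitive deficits that Aim 1a also names.

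**What to change.** In Adaptation and refinement, state that the approximately five think-aloud participants are chosen purposively:
- Reserve at least one place, preferably two, for participants with aphasia, defined as NIHSS item 9 of 1 or more. Aim also to include arm weakness (items 5a/6a). Both are already scored at baseline.
- Use in this interview the communication supports already planned for MET and app coaching, with the CPAP partner present where available.
- Set a time limit on the wait. If the minimum is not met by then, report the deficit mix and limit the final usability conclusion accordingly.
- Leave the batch of 12 consecutive and report its deficit mix. Holding it open for a quota could add participants to it.

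No cognitive quota is proposed, because the protocol lists no dedicated cognitive test with which to define one.

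The cost is protocol wording and a longer think-aloud step, at the waits worked out above. If aphasia is as uncommon as 10%, two reserved places could stall the step, hence the time limit and the option of one place. Spare capacity within the 48 should not be assumed, because the protocol says that the adaptation cycle will be repeated and does not say how many participants the repeats will use.

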(i) CPAP technical support: Initial mask fitting will be completed by the study's sleep technologist on the IPR unit rather than by respiratory therapists, if possible. The study's sleep technologist will initially ensure adequate mask fit without air leak, trial different CPAP mask interfaces for patient comfort and provide education or adjustments to address adherence issues.⁴¹ A member of the SCOUTS3 team led by the study's sleep technologist may then meet ideally daily with participants over the first three days of initiating CPAP to assess perception of treatment and symptom-related treatment response;^{42,43} complete a 7-item questionnaire of common adverse symptoms associated with CPAP (appended);⁴⁴ make mask type/size or device adjustments, as needed; and provide training to participants and CPAP partners to improve skills involved with mask placement and device maintenance. For participants with non-acceptance of CPAP over the first night, a standardized desensitization program may be implemented by the sleep technologist. Persistent problems with CPAP use, mask fit, or high residual respiratory events may be discussed between the sleep technologist and Co-I [name], a board-certified sleep medicine physician.

(ii) MET with individualized verbal and written feedback: In-person MET sessions during IPR and telephone sessions after IPR discharge will also be completed by a sleep coach. The in-person MET sessions will occur typically within 3 days of starting CPAP and again after about 3 to 5 days if the participant remains on IPR. The 1st in-person MET session will focus on subjective assessment of CPAP use, barriers and facilitators of use, assessment of motivation and confidence for use, decisional balance and feedback. The 2nd MET session will focus on subjective appraisals of CPAP adherence, reinforcement of changes with treatment, and review of treatment goals. The post-discharge MET phone sessions will begin approximately two weeks after discharge, then monthly during the 3 months of CPAP therapy and will last approximately 30-60 minutes. Consistent with prior research in stroke patients on the dose of MET needed, the goal will be to deliver a total of 4 hours of MET counseling over the 3 months of CPAP therapy.^{45,46} In the spirit of MET, the participants will dictate the pace of the sessions. We may alter the frequency, duration, and content of the sessions based on participant feedback.

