Given the no more than minimal risk nature of the study, [name] will be responsible for monitoring the safety of participants. Given the risks, only serious adverse events that are definitely, possibly, or have a reasonable possibility of being related to a study procedure will be reported to the IRB. Standard definitions of serious adverse events, relatedness, and seriousness will be used. Standard reporting scheduled will be applied.

Statistical analysis

The primary endpoint is the themes related to acceptability, feasibility, and appropriateness of the behavioral adherence intervention based upon participant and CPAP partner feedback during the semi-structured interviews. The secondary endpoint is 3-month average nightly CPAP usage.

Demographic and stroke- or sleep-related factors associated with mean CPAP use will be assessed using t-tests for dichotomous variables and linear regression for continuous variables. Additional post-hoc analysis of race/ethnicity may be completed.

Introductory Pamphlet (to be edited)

NIH Stroke Scale

NIH Stroke Scale Item	Function	Scores	Score
1a. Level of Consciousness (Alert, Drowsy, etc.)	Alert Drowsy Stuporous (requires repeated stimuli) Comatose (reflex responses only)	0 1 2 3	
1b. LOC Questions (Ask month, age)	Both correct One Correct Both Incorrect, unable to answer	0 1 2*	
1c. LOC Commands (Open, close eyes, make fist, let go)	Obeys both correctly Obeys one correctly Both Incorrect, unable to perform*	0 1 2*	
2. Best Gaze (Eyes open-patient follows examiner's finaer or race)	Normal Partial gaze palsy (for coma see Forced deviation Note 2 below)	0 1 2	
3. Visual (Introduce visual stimulus threat to patient's visual field quadrants)	No loss Partial hemianopia (for coma see Complete hemianopia Note 3 below) Bilateral hemianopia	0 1 2 3	
4. Facial Palsy (Show teeth, raise eyebrows and squeeze eyes shut)	Normal Minor asymmetry Partial (lower face paralysis) Comotole*	0 1 2 3*	
5a. Motor Arm-Left (Elevate extremity 90 degrees When sitting and score drift/movement)	No drift Drift Some effort against gravity No effort against gravity No movement"	0 1 2 3 4**	
5b. Motor Leg-Left (Elevate extremity 30 degrees When lying down and score drift/movement)	No drift Drift Some effort against gravity No effort against gravity No movement*	0 1 2 3 4*	

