6. I use the CPAP treatment because it feels good to use CPAP.	Strongly agree 5	Agree 4	Undecided 3	Disagree 2	Strongly disagree 1
7. I use the CPAP treatment because other people say I have to.	Strongly agree 5	Agree 4	Undecided 3	Disagree 2	Strongly disagree 1
8. I use the CPAP treatment because the personnel say I have to.	Strongly agree 5	Agree 4	Undecided 3	Disagree 2	Strongly disagree 1
9. I use the CPAP treatment because I have to.	Strongly agree 5	Agree 4	Undecided 3	Disagree 2	Strongly disagree 1

Prestroke sleep duration & Quality (baseline in reference to pre-stroke state)

Sleep duration:

During the month prior to the stroke, excluding naps, how many hours of actual sleep did you get at night (or day, if you work at night) on average?

RESPONSE OPTIONS: < 6 hours per night, 6-8 hours per night, > 8 hours per night

Sleep quality:

During the month prior to your stroke, how would you rate your sleep quality overall?

RESPONSE OPTIONS: 1 = excellent, 2 = very good, 3 = good, 4 = fair, 5 = poor

Prestroke sleep duration & Quality (90 day)

Sleep duration:

During the past month, excluding naps, how many hours of actual sleep did you get at night (or day, if you work at night) on average?

RESPONSE OPTIONS: < 6 hours per night, 6-8 hours per night, > 8 hours per night

Sleep quality:

During the past month, how would you rate your sleep quality overall?

RESPONSE OPTIONS: 1 = excellent, 2 = very good, 3 = good, 4 = fair, 5 = poor

After Nox T3 sleep apnea test

Was the T3 qualifying for CPAP treatment (REI ≥ 5 and CAI was $<50\%$ of REI)?

RESPONSE OPTIONS: yes, no, sufficient data not obtained

If yes,

Did the participant try CPAP for at least one night?

RESPONSE OPTIONS: yes, no

Participant phone number:

Participant email:

Participant address:

Did the participant identify a CPAP partner?

RESPONSE OPTIONS: yes, no

If yes,

CPAP partner name

CPAP partner phone number

7 adverse symptoms of CPAP (after night 1, night 2 and night 3 of using CPAP)

“Did you have problems with CPAP last night?”

No **Yes**

“We would like you to answer yes or no to some **side effects** of CPAP that people may experience.”

List of 7 adverse events or problems associated with CPAP use

Patient receives a score of one point for the presence of any complaints within each category, producing a total possible side effect score of seven points.

Mouth dryness

Nasal symptoms

Eye problems

Claustrophobia

Noise problems

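### Does the usage endpoint need a stated rule for participants who qualify for CPAP but never try it?

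*Combined protocol and SAP*

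**What the plan says.** The Statistical analysis section makes interview themes the primary endpoint and then adds: "The secondary endpoint is 3-month average nightly CPAP usage". One further sentence uses the same quantity: "Demographic and stroke- or sleep-related factors associated with mean CPAP use will be assessed using t-tests" for two-level factors, with linear regression for continuous ones. Neither sentence names an analysis set.

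Other places bear on who is in that average:

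- Screening for OSA starts from 60 tested participants and expects about 20% to be excluded, "yielding approximately 48 participants for the Aim 1 adherence program adaptation".
- Protection Against Risk removes enrolled participants after the sleep test for predominant central apnea or absence of OSA. Declining CPAP is not one of these grounds.
- The form completed after the sleep test asks of those who qualify: "Did the participant try CPAP for at least one night".
- The Overview describes the intervention as "beginning during IPR and extending for 3 months". The MET description schedules phone sessions two weeks after discharge, "then monthly during the 3 months of CPAP therapy".
- Adaptation and refinement gives usage a role during the study: "Analysis of participant, CPAP partner and staff interviews along with adherence and engagement data will feed Discovery". It continues: "The adapted intervention will be tested on the next 12 participants over an estimated 4 months".

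**The concern.** The study foresees the never-user and records that person, yet does not say how they enter the mean. Two readings are possible. In one, everybody who qualifies is in the denominator and a never-user contributes 0. In the other, the mean describes only people who had a period of CPAP therapy, and never-users drop out.

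The choice can change the direction of a result as well as its level. Suppose an adaptation persuades reluctant patients to start, and they use the device for less time than those who were already using it. The first mean goes up and the second goes down. Because adherence data inform the adaptation cycle, a genuine improvement in uptake could be read as a decline. The factor analyses are exposed in a similar way: a factor that acts only by keeping people from starting can be detected under the first reading and is invisible under the second.

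**Working it through.** **Reproducing the plan's figure.** 60 × (1 − 0.20) = 48 qualifying participants, as stated. The documents give no expected hours, SD, never-try rate or alpha, so every hour and rate below is an assumption for illustration.

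**Effect on the level.** Let n qualify, r of them never try CPAP, and the triers average m hours. Counting never-users gives m(n − r)/n; leaving them out gives m. The relative difference is r/n, whatever m is. With n = 48 and m = 4 h:

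| Never-users r | Share r/48 | Counted as 0 | Left out |
|---|---|---|---|
| 3 | 6.25% | 4 × 45/48 = 3.75 h | 4.00 h |
| 6 | 12.5% | 4 × 42/48 = 3.50 h | 4.00 h |
| 12 | 25% | 4 × 36/48 = 3.00 h | 4.00 h |

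**Effect on direction.** Let k of the r refusers start, at c hours each.

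- Mean over all qualifiers changes by +kc/n.
- Mean over triers changes by −k(m − c)/(n − r + k).

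The signs are opposite exactly when 0 < c < m. If c = m the trier mean does not move; if c > m both rise.

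- n = 48, r = 12, k = 6, m = 4, c = 1.5: all qualifiers 144/48 = 3.00 to 153/48 = 3.19 h (+0.19); triers 4.00 to 153/42 = 3.64 h (−0.36).
- Batch of 12, r = 3, k = 2, same m and c: all qualifiers 36/12 = 3.00 to 39/12 = 3.25 h (+0.25); triers 4.00 to 39/11 = 3.55 h (−0.45).
- Batch of 12, r = 3, all three start at c = 2: all qualifiers 3.0 to 42/12 = 3.5 h; triers 4.0 to 42/12 = 3.5 h.

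**Effect on the factor t-tests.** Simulation with 40,000 runs, 24 versus 24 participants, triers normal with mean 4 h and SD 2 h floored at 0, never-use drawn at random for each participant, pooled t-test at 5%:

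| Never-try rates | Significant, counted as 0 | Significant, left out |
|---|---|---|
| 33% vs 8% | 31% | 5% |
| 25% vs 8% | 17% | 5% |
| 17% vs 8% | 8% | 5% |
| equal (5/24 each) | 5% | 5% |

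Both readings hold the nominal 5% when the rates are equal. Even at the widest contrast, about 69% of runs show nothing when never-users are counted.

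**Which reading the text supports.** The only wording that favours omission is the reference to months of CPAP therapy, and that phrase sets the timing of counselling calls. It says nothing about who is analysed. The expected 48 are described as the adaptation group as a whole, and the listed post-enrollment exclusions do not include refusal. A nightly average over three months for someone who never used the device is 0. The natural default is therefore all qualifiers, with never-users at 0.

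**Whether the adaptation could be misled.** The first review, at about 6 months, draws on interviews and adherence patterns and does not name the endpoint mean. By then only an estimated 8 participants will have had the 3-month interview, so the 3-month average is barely available. The later batch is 12 people, with a field showing who tried CPAP. A team reviewing that few people would see refusers starting.

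**The case for a change.** The best argument for a change is that being able to compute both summaries later is a reason to name one beforehand. The protocol's background complains that larger stroke trials left out people with poor early adherence, and silently dropping never-users would repeat that selection. The intervention includes desensitization for patients who do not accept CPAP on the first night, so uptake is part of what it tries to change. The planned randomized trial will measure adherence, and a clear definition here would carry over.

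Much of this stands. The rule is absent, the sign reversal is correct algebra, and a sentence naming the analysis set would do no harm. The argument falls short on consequence. Nothing the plan states produces a wrong answer. A real gain would be mistaken for a loss only if the team relied on the trier mean alone and ignored its own record of who tried CPAP. The two t-test readings answer different questions, one about use including uptake and one about hours among starters, and neither is biased for its own question. The randomized trial is left to a separate application, where its endpoint can be defined.

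**Conclusion.** The omission is genuine but is missing detail of a kind that analysts fill sensibly, and no change to the plan follows. The other sections lean toward all participants with a qualifying test, never-users at 0, and the form together with the device data lets a report give that mean, the number who never tried and the mean among triers side by side.

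The size is bounded. The two means differ by the never-user share, 2.1% per person among 48. They move in opposite directions only if new starters use CPAP for less time than existing users; in the examples above the shifts are between 0.19 and 0.50 h. The chance of a significant factor test differs by 3 to 26 percentage points (8% − 5% to 31% − 5%) under the assumed never-try rates. All of these hours and rates are assumptions, since the documents give none.

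The conclusion rests on the endpoint staying descriptive and secondary in a single-arm study, with no batch comparison and no test of the mean against a target. It would need another look if usage were made a formal criterion for accepting or rejecting an adaptation.
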